11.2.1.3. Part B (Cold Urticaria Subjects)

Day:	Screening	-1	1	2	3	4	Follow-up	Notes
Visit Window (relative to Day 1)	-28 to -7 days						Day 5 to Day 7 after last dose	
Admission to Unit		X						
Informed Consent	X							
Demographics	X							
Complete physical	X						X	
Body weight (kg)	X							
Height (cm) without shoes	X							
Brief physical		X						
Medical/medication/drug/alcohol history	X							

Day:	Screening	-1	1	2	3	4	Follow-up	Notes
Visit Window (relative to Day 1)	-28 to -7 days						Day 5 to Day 7 after last dose	
12-lead ECG ¹	X	X			X		X	1. Triplicate ECG at screening and CV risk factors questionnaire
Vital signs	X	X	X	X	X		X	
Urine drug/alcohol screen	X	X						
Pregnancy Test (women) ²	X(S)		X(S/U)				X(S)	2. Pregnancy test will be performed 3 times during screening, serum on day -28, day -7 to -4, and a serum or urine pregnancy test the day of the start of the study prior to dosing and a serum pregnancy test at the follow up visit
HIV, Hep B and Hep C screen	X							
Clinical Laboratory Tests	X	X			X		X	
Allergen Challenge- SPT	X ^{4,5}		X ^{4,6}		X ^{4,6}			4. SPT- Skin Prick Test measurements will be performed ~15-20mins post challenge 5. SPT using all 4 specified allergens 6. SPT will be performed at 6 hours post dose (see Clinical Trial Protocol Section 6.4.1)
TSH ³	X							3. TSH test only at screening only
Cold Temp Test (Temp Test 4.0)	X		X		X	X ⁷		7. 24 hours after last dose
Review of eligibility criteria and medication prior to randomisation		X						
Randomisation		X						
Tolerability Assessment			X ¹⁰ ←-----→					10. Tolerability assessment at pre – and ~6 hours post-dose
AE assessment		X	←-----→			X		
Concomitant Medication		X	←-----→			X		

Day:	Screening	-1	1	2	3	4	Follow-up	Notes
Visit Window (relative to Day 1)	-28 to -7 days						Day 5 to Day 7 after last dose	
Pharmacokinetic Blood Sample ⁸			X		X	X ⁹		8. PK blood sample taken at pre dose, 1, 2, 4, 8, 12hr post dose 9. If only once daily dosing then a PK sample will be taken at 24h post dose
Study Treatment Dosing			X	X	X			
Discharge from unit						X		
Outpatient visit	X						X	

11.2.1.4. Part C (Chronic Spontaneous Urticaria Cohort)

Day:	Screening	1	2	3	4	5	6	7	Follow-up	Notes
Visit Window (relative to Day 1)	-28 to -7 days								9-14 days after last dose	
Informed Consent	X									
Demographics	X									
Complete physical	X							X		
Body weight (kg)	X									
Height (cm) without shoes	X									
Brief physical		X						X		
Medical/medication/drug/alcohol history	X									
12-lead ECG ¹	X	X					X	X		1. Triplicate ECG at screening and CV risk factors questionnaire
Vital signs	X	X		X		X		X		
Urine drug/alcohol screen	X	X								

Day:	Screening	1	2	3	4	5	6	7	Follow-up	Notes
Visit Window (relative to Day 1)	-28 to -7 days								9-14 days after last dose	
Pregnancy Test (women) ²	X(S)	X (S/U)							X(S)	2. Pregnancy test will be performed 3 times during screening, serum (S) on day -28, day -7 to -4, and a serum or urine (U) pregnancy test the day of the start of the study prior to dosing and a serum pregnancy test at the follow up visit
HIV, Hep B and Hep C screen	X									
Clinical Laboratory Tests	X	X					X	X		
TSH ³	X									3. TSH test only at screening only
Blood Sample for CD69 expression ¹¹		X ⁹						X ¹⁰		9. Predose 10. 4 hours post dose 11 A decision will be made after Part A on whether samples are taken in Part C
Randomisation	X									
UAS-7 Diary ⁴	X	X	X	X	X	X	X	X		4. Screening UAS7 diary will be completed using 7 successive days before randomisation (day 1). If there is a lapse in any day prior to day 1 the subject must complete the full 7 days worth of diary entries again during the screening period.
QOL (DLQI)	X	X						X		
AAS	X	X	X	X	X	X	X	X		
AE assessment		X ⁸ ←-----→						X		8. Tolerability assessment at pre – and post-dose

CONFIDENTIAL

200196

Day:	Screening	1	2	3	4	5	6	7	Follow-up	Notes
Visit Window (relative to Day 1)	-28 to -7 days								9-14 days after last dose	
BHR- Basophil Histamine Release Test		X ⁵								5. Sample taken predose
Pharmacokinetic Blood Sample ⁶		X			X			X		6. PK blood sample taken at pre-dose sample and 2 and 4hr post dose
Study Treatment Dosing		X	X ⁷	X ⁷	X	X ⁷	X ⁷	X		7. The nurse will visit the subject at home to apply the dose
Outpatient visit	X	X			X			X	X	

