Immune cell effects, including neutropenia	
SYK is involved in immunoreceptor signalling in a number of cell types, including mast cells, basophils, B cells, neutrophils and macrophages (Riccaboni, 2010)
 
Studies with R788 in rheumatoid arthritis identified an increased risk of neutropenia in subjects treated with the oral SYK inhibitor compared to placebo (placebo 0.7%, R788 150mg OD 6.6%, R788 100mg BD 5.9%) (Weinblatt, 2010)
	Subjects with co-morbid conditions that would put them at risk or laboratory values outside the reference range at screening would be excluded from participating in the study.	
The product is being investigated in a topical formulation, which should limit potential systemic exposure. Increasing exposure will be performed gradually.
 
Subjects will undergo regular haematological assessments, including white blood cell counts during the study.
 
Treatment would be stopped if laboratory test results are identified that would put the safety of the subject at risk.

Thyroid	Minimal thyroid follicular epithelial hypertrophy was observed in all doses following iv administration of GSK2646264 in rats for 4 weeks. Thyroid function test (TSH, free and total T3 and T4) at single timepoints 12 hours post last dose were within normal range.	Requirement for normal TSH in all subjects in Part A, and normal TSH, free T4, T4 and T3 in Parts B and C.. Exclusion of subjects with history of Graves' disease or any thyroid cancer	The risk of thyroid effect in this study is considered not to be significant. Monitoring will be based on signs and symptoms and serum markers of thyroid function will be measured in patients in Parts B and C.

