### 6.1.3. Part B: Cold urticaria Subjects Time and Event table

Day:	Screening	-1	1	2	3	4	Day 6 to 15	Follow-up (Day 17-19)	Notes
Visit Window (relative to Day 1)	-28 to -7 days 								1. Screening can occur on any day between 28 days and 7 days prior to Day 1 dosing.
Admission to Unit		X							
Informed Consent	X								
Demographics	X								
Complete physical	X							X	
Body weight (kg)	X								
Height (cm) without shoes	X								
Brief physical		X							
Medical/medication/drug/alcohol history	X								
12-lead ECG	X 	X			X			X	2. Triplicate ECG at screening and CV risk factors
Vital signs 	X	X	X	X	X		X	X	3. Should be performed at the same time points as PK samples are taken
Urine drug/alcohol screen	X	X							
Pregnancy Test (women) 	X(S)		X(S/U)			X (S)	X(S)		4. Pregnancy test will be performed 3 times during screening, serum on day -28, day -7 to -4, and a serum or urine pregnancy test the day of the start of the study prior to dosing and a serum pregnancy test between day 10-12 (to coincide with a PK sample) and at the follow up visit.
HIV, Hep B and Hep C screen	X								
Clinical Laboratory Tests	X	X			X			X	

Day:	Screening	-1	1	2	3	4	Day 6 to 15	Follow-up (Day 17-19)	Notes
Allergen Challenge-SPT	X 		X 		X 	X 			5. SPT- Skin Prick Test measurements will be performed ~15-20mins post challenge 6. SPT using all 4 specified allergens 7. SPT will be performed at 6 hours post dose (see Section 6.4.1), and at 24 hours post last dose on day 3 8. SPT will be performed pre-dose on Day 1
TSH, free T4, T4, T3	X					X	X 	X	9. One sample between day 10-12 to coincide with PK sample
Cold Temp Test (Temp Test 4.0)	X		X 		X 	X 			10. Pre-dose 11. 6 hours post dose 12. 24 hours post last dose on Day 3
Randomisation		X							
Tolerability Assessment			←-----X  -----→						13. Tolerability assessment at pre – and ~6 hours post-dose
AE assessment			←-----X-----→				X		
Concomitant Medication		X	←-----X-----→				X		
Pharmacokinetic Blood Sample			X 	X 	X 	X 	X 	X	14. PK blood sample taken at pre dose, 1, 4, 8, 12hr post dose 15. One PK sample to be taken 24 hours post last dose on Day 3 16. One PK blood sample per day will be taken as follows: PK samples will be obtained on the following days (± 1 day): Day 6, 9, 12, & 15.

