### 6.1.4. Part C: Chronic Spontaneous Urticaria Cohort

Day:	Screening	1	2	3	4	5	6	7	8	Day 10 ( $\pm$ 1 day)	Day 15 ( $\pm$ 1 day)	Follow-up Day 22 ( $\pm$ 1 day)	Notes
Visit Window (relative to Day 1)	-28 to -7 												1. Screening can occur on any day between 28 days and 7 days prior to Day 1 dosing.
Informed Consent	X												
Demographics	X												
Complete physical	X											X	
Body weight (kg)	X												
Height (cm) without shoes	X												
Brief physical		X											
Medical/medication/drug/alcohol history	X												
12-lead ECG	X 	X						X				X	2. Triplicate ECG at screening and CV risk factors
Vital signs	X	X		X			X			X 	X 	X 	3. To be performed on same day as PK samples
Urine alcohol screen	X	X											
Pregnancy Test (Women of child bearing potential) 	X(S) 	X (U) 						X(U) 		X (S)	X(S)		4. A serum (S) pregnancy test will be performed on the day of screening. If the day of screening is between Days -13 and -7, a further pregnancy test will not be required until Day 1. However, if the day of screening is between Days -28 and -14, an additional serum pregnancy test will be required between Days -7 and -4.

Day:	Screening	1	2	3	4	5	6	7	8	Day 10 ( $\pm$ 1 day)	Day 15 ( $\pm$ 1 day)	Follow-up Day 22 ( $\pm$ 1 day)	Notes
													5. A urine pregnancy test is required prior to dosing on Day 1 & Day 7
HIV, Hep B and Hep C screen	X												
Clinical Laboratory Tests	X	X						X				X	
TSH, free T4, T4, T3	X							X		X6	X6	X6	6. Sample to be taken on same day as PK sample
Blood Sample for CD69 expression		X 		X 		X 			X 	X 	X 		7. Pre-dose 8. 4 hours post dose 9. Sample to be taken on same day as PK sample
Randomisation		X											
UAS-7 Diary	X 		X 	X					10. Screening UAS7 diary will be completed for the 7 successive days before Randomisation (Day 1). If there is a lapse in any day prior to Day 1 the subject must complete the full 7 days worth of diary entries again during the screening period. 11. The UAS-7 diary should be completed pre-dose on those days where dosing occurs				
QOL (DLQI)	X	X 							X				12. The baseline DLQI assessment on Day 1, looking back over the previous 7 days prior to dosing, should be completed pre-dose

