### Clinical Chemistry

BUN	Potassium	AST (SGOT)	Total and direct bilirubin
Creatinine	Chloride	ALT (SGPT)	Albumin
Glucose, (fasting at screening only)	Calcium	GGT	Total Protein
Sodium	Phosphate	Alkaline phosphatase	
TSH , free T4, T4, T3			

NOTE: Details of Liver Chemistry Stopping Criteria and Follow-Up Procedures are given in Section 5.7.1.

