Urine for metabolite analysis			X ¹⁰			X ²²						10. Pre dose and pool samples taken 0-12 and 12-24 hours post dose 22. Pool samples taken 0-12 and 12-24 hours post
HIV, Hep B and Hep C screen	X											
Clinical Laboratory Tests	X ¹⁷	X ¹⁷		X ⁹		X ⁹	X ¹⁷		X ¹⁷	X ¹⁷		9. Pre-dose AST, ALT, Alkaline Phosphatase, Total Bilirubin Only- : results to be communicated to the GSK Medical monitor on the same day 17.Clinical lab test as per Section 6.3.4 of the protocol

Day:	Screening	-1	1	2	3	4	5	6	7	8	Follow-up	Notes
Visit Window (relative to Day 1)	-28 to -7									Day 9 – Day 11		
Allergen Challenge- Skin Prick Test	X ^{3,4}		X ^{3,5}		X ^{3,5}	X ^{3,5}		X ^{3,7}			3. SPT- Skin Prick Test measurements will be performed ~15-20 mins post challenge. 4. SPT with all 4 specified allergens 5. SPT will be performed 6 hours post dose 7. SPT will be performed 48 hours post dose of Day 4 (on the morning of Day 6)	
TSH ²	X										2. TSH test only at screening only	
Randomisation		X										
Tolerability Assessment			X ¹¹ ←-----→ only on dosing days 1 to 4								11. Tolerability assessment at pre – and ~6 hours post-dose on dosing days	
AE assessment		X								X		
Concomitant Medication		X								X		
Pharmacokinetic Blood Sample			X ⁶	X ⁶	X ⁶	X ⁶	X ¹⁸	X ¹⁹	X ²⁰	X ²¹	6. PK blood sample taken at pre dose, 1, 2, 4, 8, 12 and 24hours post previous dose 18. PK blood sample taken at 30, 36, 48 hours, post dose of Day 4 19. PK blood sample taken at 54, 60, 72 hours, post dose of Day 4 20. PK blood sample taken at 78, 84 hours post dose of Day 4 21. PK blood sample taken at 96 hours post dose of Day 4	

Day:	Screening	-1	1	2	3	4	5	6	7	8	Follow-up	Notes
Visit Window (relative to Day 1)	-28 to -7									Day 9 – Day 11		
Blood Sample for CD69 expression			X ¹²			X ¹³	X ¹⁴		X ¹⁵	X ¹⁶		12. Predose 13. 4 hours post dose of Day 4 14. 24 hours post dose of Day 4 (sample taken in the morning of day 5) 15. 72 hours post dose of Day 4 16. 96 hours post dose of Day 4
Study Treatment Dosing ⁸			X	X	X	X						8. This will be once daily dosing using fresh bottles at 1% strength in the morning
Discharge from unit										X		
Outpatient visit	X										X	

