11.6. Appendix 6: Values of Potential Clinical Importance

11.6.1. Laboratory Values

Haematology				
Laboratory Parameter	Units	Category	Clinical Concern Range	
			Low Flag (< x)	High Flag (>x)
Hematocrit	Ratio of 1	Male		0.54
		Female		0.54
		Δ from BL	↓ 0.075	
Hemoglobin	g/L	Male		180
		Female		180
		Δ from BL	↓ 25	
Lymphocytes	x10 ⁹ / L		0.8	
Neutrophil Count	x10 ⁹ / L		1.5	
Platelet Count	x10 ⁹ / L		100	550
White Blood Cell Count (WBC)	x10 ⁹ / L		3	20
Red Blood Cell Count (RBC)	x10 ⁶ cells/µL		4.2	5.9
Mean Corpuscular Volume (MCV)	fL		80	100
Mean Corpuscular Hemoglobin (MCH)	pg		28	32
Mean Corpuscular Hemoglobin Concentration (MCHC)	g/L		32	36
Monocytes	x10 ⁹ / L			0.208
Eosinophils	x10 ⁹ / L			0.44
Basophils	x10 ⁹ / L			0.01

Clinical Chemistry				
Laboratory Parameter	Units	Category	Clinical Concern Range	
			Low Flag (< x)	High Flag (>x)
Albumin	g/L		30	
Calcium	mmol/L		2	2.75
Creatinine	mmol/L			1.3*ULN
	µmol/L			159
	µmol/L	Δ from BL		44
Glucose	mmol/L		3	11.1
Potassium	mmol/L		3	5.5
Sodium	mmol/L		130	150

Liver Function				
Test Analyte	Units	Category	Clinical Concern Range	

Liver Function			
Test Analyte	Units	Category	Clinical Concern Range
ALT/SGPT	U/L	High	$\geq 2x$ ULN
AST/SGOT	U/L	High	$\geq 2x$ ULN
AlkPhos	U/L	High	$\geq 1.5x$ ULN
T Bilirubin	$\mu\text{mol}/\text{L}$	High	$\geq 1.5x$ ULN
T. Bilirubin + ALT	$\mu\text{mol}/\text{L}$ U/L	High	$1.5x$ ULN T. Bilirubin + $\geq 2x$ ULN ALT
Urea Nitrogen (BUN)	mmol/L	Low	<2.9
Urea Nitrogen (BUN)	mmol/L	High	>7.1
Chloride	mmol/L	Low	<98
	mmol/L	High	>106
Gamma-glutamyl Transpeptidase (GGT)	U/L	Low	<8
	U/L	High	>78
Direct Bilirubin	$\mu\text{mol}/\text{L}$	High	>5.1
Total Protein	g/L	Low	<60
	g/L	High	>78

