11.10.12. ICH Listings

ICH : Listings					
No.	Population	IDSL / TST ID / Example Shell	Title	Programming Notes	Deliverable [Priority]
Randomisation					
1.	Safety	CP_TA1	Listing of Randomised and Actual Treatments		IA [1], SAC [1]
Subject Disposition					
2.	Safety	ES7	Listing of Reasons for Screen Failure		IA [1], SAC [1]
3.	Safety	ES2	Listing of Reasons for Withdrawal		IA [1], SAC [1]
4.	Safety	DV2	Listing of Important Protocol Deviations		IA (SAC)
5.	Safety	ES2	Listing of Exclusions from Per Protocol Population		IA (SAC)
Inclusion and Exclusion Criteria					
6.	Safety	IE3	Listing of Subjects with Inclusion/Exclusion Criteria Deviations		IA [1], SAC [1]
Demographics					
7.	Safety	DM2	Listing of Demographic Characteristics		IA [1], SAC [1]
8.	Safety	DM9	Listing of Race		IA [1], SAC [1]
Medical History					
9.	Safety	MH2	Listing of Medical History		IA [1], SAC [1]
Concomitant Medication					
10.	Safety	CP_CM3	Listing of Concomitant Medication by Generic Term		IA [1], SAC [1]
Study Drug Exposure					
11.	Safety	EX3	Listing of Exposure Data	If applicable adapt to study data	IA [1], SAC [1]

ICH : Listings					
No.	Population	IDSL / TST ID / Example Shell	Title	Programming Notes	Deliverable [Priority]
Adverse Events					
12.	Safety	AE7	Listing of All Adverse Events		IA [1], SAC [1]
13.	Safety	CP_AE8	Listing of Subject Numbers for Individual Adverse Events		IA [1], SAC [1]
14.	Safety	CP_AE8a	Listing of Serious Adverse Events		IA [1], SAC [1]
15.	Safety	CP_AE8	Listing of Adverse Events Leading to Withdrawal from Study		IA [1], SAC [1]
Clinical Laboratory Assessments					
16.	Safety	CP_LB5	Listing of Haematology Abnormalities of Potential Clinical Importance		IA [1], SAC [1]
17.	Safety	CP_LB5	Listing of All Haematology Laboratory Data for Subjects with Abnormalities of Potential Clinical Importance	Including change from Baseline	IA [1], SAC [1]
18.	Safety	CP_LB5	Listing of Clinical Chemistry Abnormalities of Potential Clinical Importance		IA [1], SAC [1]
19.	Safety	CP_LB5	Listing of Clinical Chemistry Laboratory Data for Subjects with Abnormalities of Potential Clinical Importance	Including change from Baseline	IA [1], SAC [1]
20.	Safety	CP_LB5	Listing of All Hematology Laboratory Data for Subjects with Adverse Events of Interest		IA [1], SAC [1]
21.	Safety	UR2b	Listing of Urinalysis Data for Subjects with Abnormalities of Potential Clinical Concern		IA [1], SAC [1]
Electrocardiogram (ECG)					

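### The SAP still schedules thyroid testing in Parts B and C as one screening TSH, so the post-dose thyroid panels in the current protocol have no SAP time points, no numeric summary by treatment, and no laboratory listing that a thyroid value can trigger

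*SAP*

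**What the plan says.** **SAP.** Sections 11.2.1.3 (Part B) and 11.2.1.4 (Part C) each have one thyroid row, marked at screening and noted "TSH test only at screening only". Free T4, T4 and T3 do not appear in the SAP. Section 1 says that the plan rests on protocol Amendment 2. Sections 3.2, 7.1.1 and 11.10.3 make it the plan for the final analysis and for safety in Parts A, B and C.

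**Protocol (Amendment 5).** The Part B schedule (6.1.3) has a row for TSH, free T4, T4 and T3 at screening, Day 4, once in the Day 6 to 15 block ("One sample between day 10-12 to coincide with PK sample") and follow-up. The Part C schedule (6.1.4) has the same four analytes at screening, Day 7, Day 10, Day 15 and Day 22, the last three noted "Sample to be taken on same day as PK sample". Table 6 gives thyroid its own risk row and states that "serum markers of thyroid function will be measured in patients in Parts B and C". Section 6.3.4 lists "TSH , free T4, T4, T3" in the clinical chemistry panel.

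**SAP displays that could apply.** Appendix 10 plans two generic chemistry tables. Table 3.9 shows absolute values and change from baseline, with an instruction to show only a Total column. Table 3.10 counts values outside the reference range. Listing 18 shows chemistry abnormalities of potential clinical importance. Listing 19 is the "Listing of Clinical Chemistry Laboratory Data for Subjects with Abnormalities of Potential Clinical Importance".

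**The concern.** Clinical laboratory safety tests are part of the primary endpoint, and thyroid is one of the risks that the protocol singles out. The Cmax NOEL of about 16 ng/mL comes from a thyroid finding in rats (protocol 3.2.2), and the same value is the Cmax threshold in protocol 5.8.1. Post-dose thyroid sampling entered with Amendment 3 because elimination was slower than expected.

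The document that specifies the final safety displays contradicts the current protocol on this test. It names one analyte of four and no visit after dosing. A programmer working from it has no instruction on which thyroid visits to summarise, whether thyroid counts as chemistry, or how to show active against placebo. At stake is how clearly the final report can show thyroid results by treatment and by subject.

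**Working it through.** No power or sample-size calculation is involved, and the plan states no figure to reproduce. The check sets the schedules side by side and then follows the results through the SAP's displays.

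**1. Time points after dosing starts**

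| | Protocol | SAP |
|---|---|---|
| Part B | Day 4, Day 10-12, follow-up Day 17-19: 3 | 0 |
| Part C | Days 7, 10, 15, 22: 4 | 0 |
| Analytes | TSH, free T4, T4, T3 | TSH (screening) |

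Day 7 in Part C is a dosing day. The table does not say whether the thyroid sample precedes the third dose, but it follows two doses either way.

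**2. Follow-up visits**
- Part B: the SAP has follow-up 5-7 days after the last dose on Day 3, so Day 3 + 5 = 8 to 3 + 7 = 10. The protocol has Day 17-19. There is no overlap.
- Part C: the SAP has 9-14 days after the last dose on Day 7, so Day 16-21. The protocol has Day 22 plus or minus 1, so Day 21-23. Only Day 21 is common.
- The SAP schedule has no Part C visit at Day 10 or Day 15.

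**3. Amount of data concerned.** Planned numbers are 12 in Part B and 16 in Part C (protocol 9.2), allocated 3:1 (5.4), so 9:3 and 12:4.
- Part B: 12 x 3 = 36 sampling occasions.
- Part C: 16 x 4 = 64.
- Total: 36 + 64 = 100, of which 9 x 3 + 12 x 4 = 75 are on active and 3 x 3 + 4 x 4 = 25 on placebo.

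This assumes complete data. It counts results without a SAP time point, not results lost.

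**4. Which displays can hold them**
- *Classification.* Protocol 6.3.4 puts the four analytes in chemistry. A note in the SAP's Part A group 2 schedule points there ("17.Clinical lab test as per Section 6.3.4 of the protocol"), but for Parts B and C the SAP keeps TSH in a row separate from the clinical laboratory tests and never says that thyroid is chemistry.
- *Table 3.9.* With a Total column only, the displayed mean change in Part B would be (9a + 3p)/12 = 0.75a + 0.25p, where a and p are the active and placebo mean changes. In Part C it would be (12a + 4p)/16, the same weights. The treatment difference a - p cannot be read from it.
- *Table 3.10.* It carries no Total-only note. With the High/Low rule in SAP 11.4.1, it would count subjects outside the reference range. It would not identify them.
- *Listings 18 and 19.* Entry depends on a "Clinical Concern Range" in SAP 11.6.1. That section covers albumin, calcium, creatinine, glucose, potassium, sodium and a liver table that also holds urea, chloride, GGT, direct bilirubin and total protein. There is no thyroid analyte, so a thyroid value cannot trigger either listing.
- *Baseline.* SAP 11.3.2 uses screening for Part C laboratory data. For Part B it uses Day -1, falling back to screening if Day -1 is missing. The protocol's thyroid row has no Day -1 sample, so screening is the baseline in both parts.

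**The case against.** The strongest reply is that this is a version mismatch and not a decision about thyroid analysis. Screening-only TSH matched the protocol before Amendment 3. SAP 11.2.1 presents its tables as the protocol's schedule, and much of its Part B and C content is out of date in the same way. That stands as the cause. It does not remove the gap: this SAP also covers the final analysis, its list of changes in 2.1 does not mention thyroid, and no later SAP is among the documents. Whether one exists cannot be told from them.

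A reader might draw four stronger conclusions, none of which the documents support:

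- *Out-of-range thyroid values would go unflagged.* If thyroid is chemistry, Table 3.10 counts them. An abnormality that the investigator judges clinically significant is an adverse event under protocol 7.1.3 and would appear in Listing 12. Listing 19 would also show thyroid values for a subject flagged on another chemistry analyte.
- *Change from baseline cannot be shown.* The baseline rules in 11.3.2 already yield screening, and Table 3.9 includes change from baseline.
- *The trial could not support what it says on thyroid safety.* The Table 6 statement is a prospective risk judgement, not a planned conclusion, and Amendment 3 records that the thyroid risk-benefit had not changed.
- *The post-dose results would be lost.* They are collected. The SAP does keep unscheduled visits out of summary tables, but its rule on visits outside the time windows refers to the protocol's windows. Nothing says that these panels are dropped.

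It is also fair that 11.6.1 is not exhaustive. Phosphate is in the protocol panel and has no limit there, so a missing thyroid limit is not an error in itself. It matters here because thyroid is a named risk and the chemistry listings depend on those limits. SAP Table 3 marks chemistry as listed, but Appendix 10 narrows this to flagged abnormalities or flagged subjects.

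**Conclusion.** The point holds in a limited form. The SAP was not updated for the thyroid sampling added by Amendment 3 and contradicts the current protocol on it: 0 post-dose time points against 3 in Part B and 4 in Part C, and one analyte against four. At best the results reach the generic chemistry tables. There the numeric summary would merge active and placebo, and the out-of-range table would give counts only. No laboratory listing is triggered by a thyroid value.

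This rests on two assumptions: that thyroid is treated as chemistry, which is an inference from protocol 6.3.4 and is not stated in the SAP, and that no later SAP replaces this one. If thyroid is not treated as chemistry, the SAP has no post-dose display for it apart from adverse events. The consequence is unclear and incomplete presentation of a named risk, not lost data. It should be corrected before the final analysis.

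**What to change.** - In SAP 11.2.1.3 and 11.2.1.4, replace the screening-only TSH row with the current protocol's TSH, free T4, T4 and T3 time points, including its follow-up windows.
- State that the four analytes are part of clinical chemistry. For Parts B and C, present them in Tables 3.9 and 3.10 by treatment and visit, lifting the Total-only instruction in Table 3.9. Name screening as their baseline, which 11.3.2 already gives.
- Add one by-subject listing of all Part B and C thyroid results, with values outside the laboratory reference range marked. This removes the dependence on a thyroid limit in 11.6.1.

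The cost is SAP text, a change of columns in the chemistry tables, a range marker and one listing. The data are already collected, and no protocol change or extra sampling is needed.
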